5.2 PDE5 inhibitors in patients with Fontan physiology

PDE5 inhibitors are a unique class of medication that have demonstrated utility in reducing

pulmonary vascular resistance and improving ventricular performance in patients with pulmonary hypertension and myocardial dysfunction¹³⁻¹⁷. These characteristics make them potentially attractive as a therapy for the Fontan population in which cardiac output, and thus exercise, are limited by the absence of a sub-pulmonary ventricle¹⁸. In limited short-term studies in children and adolescents with Fontan physiology, treatment with sildenafil, a three-times daily PDE5 inhibitor, has been safe and has shown a modest benefit in exercise performance and ventricular function^{11, 19}.

Given this background the FUEL trial, a large-scale randomized clinical trial (RCT), was designed and is expected to begin in the second quarter of 2016. The primary aim of the RCT is to evaluate the impact of udenafil (a twice-daily PDE5 inhibitor new to the United States) on exercise capacity in adolescents with Fontan physiology. Regardless of the outcome of the efficacy trial, longer-term safety data is imperative prior to wide-scale usage of this medication.

5.4 Rationale for Study Outcomes

Safety Data: The short-term safety data of PDE5 inhibitors in those with Fontan physiology has been established by a number of previous studies including the recently concluded Fontan Udenafil Phase I/II Trial, undertaken by a subset of PHN core sites. These data suggest that PDE5 inhibitors in general, and udenafil specifically, are safe in this population with side effects limited to those known to be associated with PDE5 inhibitor use. In the Fontan Udenafil Trial there were no serious adverse events associated with udenafil.

Pharmacodynamics: The primary and secondary PD aims of the FUEL trial are designed to evaluate the efficacy of udenafil on a number of important PD parameters. These include measures of exercise capacity, ventricular function (as measured by echocardiography), endothelial function, and biomarkers associated with heart failure. In the FUEL extension trial we will evaluate these parameters at study entrance (using end-of-study measures for those who participated in FUEL) and again at end-of-study. The durability of any improvement noted in FUEL is important, as it may help to inform clinical decisions regarding long-term therapy.

Biorepository: The response to udenafil may also be influenced by variants influencing the vascular response to udenafil. Variants in the endothelial nitric oxide synthase gene have been reported to influence the response to sildenafil in patients with erectile dysfunction, although this has not been studied for udenafil²⁰. Variation in genes that regulate the vascular, inotropic and chronotropic response to exercise may influence the exercise capacity of patients after the

Fontan procedure as well as the response to udenafil. DNA will be stored to perform future genotyping studies to analyze the genetic contribution to the response to udenafil.

Functional Health Status: In the PHN Fontan Cross-Sectional Study, physical and psychosocial functional statuses were significantly reduced across almost all domains^{21, 22}. It is clear that overall functional status is significantly reduced in this population compared to a healthy control population²³. Given these findings, a highly desirable goal of any therapy to improve or maintain function in the population with the Fontan procedure would be maintenance or improvement in overall health status. However, in the PHN study, none of the evaluated measures of exercise performance including percent of predicted maximal VO₂ significantly correlated with measures of physical functioning or psychosocial domains²². Given these findings, even a positive effect of udenafil therapy on aerobic capacity may not necessarily result in improved functional status.

Under these circumstances, any change in functional status over time that is associated with udenafil therapy would be an extremely important outcome.

6. STUDY / TRIAL DESIGN

6.1 Overview

This study is a 12-month (52 week) safety extension study, with an option for up to an additional 36 months, to supplement the FUEL Phase III clinical trial to provide a more robust safety and side-effect profile of the use of udenafil in adolescents with Fontan physiology. We will attempt to recruit all participants who completed the FUEL trial, a potential of approximately 400 subjects, and will supplement, if needed, with additional adolescents with Fontan physiology until the minimum of 300 total subjects have been enrolled.

Figure 1 Trial Schema

6.2 Study Design

This will be an open-label extension study. All enrolled subjects will be provided with udenafil, at a dose of 87.5 mg bid, for the duration of the study. Importantly, once the results of FUEL are known, these will be presented to the DSMB which will then provide a recommendation as to whether the FUEL extension trial should continue. If a total lack of efficacy is determined, the extension trial may be discontinued.

6.3 Study Measures

6.3.1 Measures of Primary Aim (Safety)

All adverse events will be collected and recorded for the duration of the trial.

6.3.2 Measures of Secondary Aims (Pharmacodynamics)

Primary Outcomes:

- Exercise: Change in maximal oxygen consumption from FUEL extension baseline (will be end-of-study testing for FUEL participants) to testing at 12 months measured using a standardized exercise test.
- Echo: Change in myocardial performance index as measured by pulse wave Doppler echocardiography from baseline to testing at 12 months.
- Endothelial Function: Change in log-transformed Reactive Hyperemia Index derived from the EndoPAT® device.
- Functional Health Status: Change in full scale Peds QL
- Biomarkers: Change in serum BNP level from baseline to testing at 12 months.

Secondary Outcomes:

- Exercise: Submaximal measures of exercise capacity will be collected and evaluated.
- Echo: Measure of systolic and diastolic function will be collected from a targeted echocardiogram.
- Functional Health Status: Change in Peds QL physical functioning score, psychosocial functioning score, and cardiac-specific quality of life score. Change in Pediatric Cardiac Quality of Life Inventory (PCQLI) score.
- Arrhythmia Burden (limited to non-FUEL subjects; participation is optional) will be assessed at 2 time points: pre-study drug and post-study drug (both during the baseline visit): Number of premature atrial or ventricular beats (2 outcomes) as a percentage of total beats over the course of heart-rhythm monitoring from pre-study drug measurements compared to taking study drug. Occurrence, duration and speed of atrial or ventricular

arrhythmias (2 outcomes), and comparison between the two time points.

6.3.3 Covariate Measures

We will attempt to identify possible associations between a variety of clinical factors and both safety and PD outcomes. Examples of clinical factors include:

- Age
- Gender
- Race/ethnicity
- Height/weight
- Ventricular morphology
- Resting oxygen saturation
- Baseline pharmacodynamic test results
- Current medication use

6.4 Study Visits

Baseline Visit – For those subjects who WERE participants in the FUEL Trial:

1. Baseline screen

Prior to study enrollment, patients will be screened to ensure that all inclusion criteria are met and none of the exclusion criteria are present. The safety labs for FUEL will be accepted as meeting the inclusion criteria for FUEL extension. Pregnancy testing for OLE will be done at every in-person visit via a urine or serum pregnancy test for female participants. If the pregnancy test is positive all further testing will be stopped, the patient will not be enrolled into the trial and the result will be conveyed to the subject and/or guardians by the site-principal investigator in accordance with local IRB procedures.

2. Informed consent

Informed consent and assent for FUEL Extension will be obtained (if not obtained prior) as per local IRB/REB requirements during the end-of-study visit for FUEL.

3. Baseline PD testing

End-of-study pharmacodynamic testing for FUEL will serve as baseline testing for FUEL Extension.

4. Quality of life surveys

End-of study quality of life survey results (Peds QL, Peds QL cardiac specific module, PCQLI), HAES for FUEL will serve as baseline testing for FUEL Extension

5. Initiation of study drug (See Table 2)

Subjects will return to their study center in the shortest period of time deemed practical, following FUEL study completion, for study drug initiation under direct observation. During this visit, a resting blood pressure and heart rate will be obtained just prior to dosing. One dose of the study medication will be administered to the subject. At approximately 2 hours (+/- 30 minutes) post dosing, an additional resting heart rate and blood pressure will be measured and the subject will be asked to perform a self-limited 6-minute walk. A repeat heart rate and blood pressure will be measured immediately following the 6 minute walk and a blood sample will be obtained for determination of udenafil and metabolite concentration. At approximately 2 hours (+/- 30 minutes) following the 6-minute walk, a final resting heart rate and blood pressure will be obtained, adverse events will be recorded, and the subject will be dispensed their initial supply of study medication. The subject will be instructed to take the medication twice a day and to bring back the medication bottle for their next in-person visit.

The subject will then be discharged from the clinic. Importantly, if the subject has a drop in systolic blood pressure > 20 mmHg from the pre- to post-6 minute walk measurement, or if the systolic blood pressure drops below the 5th percentile for age (calculated by $2 \times \text{age} + 65$), they will be excluded from receiving any further study drug. These subjects will be followed for 90 days per the FUEL protocol for adverse event monitoring.

Baseline Visit - For those subjects who WERE NOT participants in the FUEL Trial:

The baseline visit consists of two parts, baseline testing and study drug initiation. These parts may be combined into a single day, or split into two days so long as the duration of time between the visits is no more than 7 days.

1. Baseline screen

Prior to study enrollment, patients will be screened to ensure that all inclusion criteria are met and none of the exclusion criteria are present.

2. Informed consent

On the day of the first study visit, informed consent and assent will be obtained (if not obtained prior) as per local IRB requirements.

3. Baseline PD testing and safety labs

The EndoPAT® vascular assessment will be completed as the first PD test following consent. This must be performed in a fasting (from midnight until after the test), non-caffinated state. After the vascular assessment, subjects will have a targeted echocardiogram to assess ventricular function. A short break will be given, either after the vascular assessment or after the echocardiogram, and a light snack will be provided. Safety labs will be performed following the vascular assessment, echocardiogram, and break. These will include collection of blood to evaluate serum creatinine and liver enzyme (aspartate transaminase and alanine transaminase) levels for all participants, and a urine or serum pregnancy test for female participants. If the pregnancy test is positive all further testing will be stopped, the patient will not be enrolled into the trial and the result will be conveyed to the subject and/or guardians by the site-principal investigator in accordance with local IRB procedures. After the safety labs, an exercise test will be administered using a braked cycle ergometer following a ramp protocol previously published in the PHN Fontan Cross-Sectional Study³. As with the FUEL study, subjects who fail to achieve a maximal effort on a baseline exercise test will be offered an opportunity to repeat the test within a 2 week time window. After exercise testing, subjects will have completed the baseline testing.

4. Quality of life surveys

The Peds QL, cardiac specific Peds QL, HAES and PCQLI will be administered during the baseline testing visit.

5. Initiation of study drug (see Table 2)

Study drug initiation will occur under direct observation. A resting blood pressure and heart rate will be obtained just prior to dosing. One dose of the study medication will be administered to the subject. At approximately 2 hours (+/- 30 minutes) post dosing, an additional resting heart rate and blood pressure will be measured and the subject will be asked to perform a self-limited 6-minute walk. A repeat heart rate and blood pressure will be measured immediately following the 6 minute walk and a blood sample will be obtained for determination of udenafil and metabolite concentration. At approximately 2 hours (+/- 30 minutes) following the 6-minute walk, a final resting heart rate and blood pressure will be obtained, adverse events will be recorded, and the subject will be dispensed their initial

supply of study medication. The subject will be instructed to take the medication twice a day and to bring back the medication bottle for their next in-person visit. The subject will then be discharged from the clinic. Importantly, if the subject has a drop in systolic blood pressure > 20 mmHg from the pre- to post-6 minute walk measurement, or if the systolic blood pressure drops below the 5th percentile for age (calculated by 2 x age + 65), they will be excluded from receiving any further study drug. These subjects will be followed for 30 days for adverse event monitoring.

6. Baseline Visit Day 1 of 2: Heart Rhythm Monitoring pre-study drug dose

At study initiation, a subset of FUEL Extension subjects who were not in the FUEL Trial will have the opportunity to enroll in a heart rhythm-monitoring study. Heart rhythm monitoring will include a 3 to 7-day baseline monitor followed by a 3-day steady state monitor. Enrollment in the heart rhythm-monitoring arm will require that subjects split the baseline visit such that baseline testing is performed 3 to 7 days prior to drug initiation. At the conclusion of baseline testing on day 1 of 2, the heart monitor will be placed on the subject. The device will be worn for 3 to 7 days and removed when the patient returns for study drug initiation (baseline visit day 2 of 2). The device, identified only by the subject's study identification number, will then be sent to the vendor for generation of a report..

7. Baseline Visit Day 2 of 2: Heart Rhythm Monitoring after study drug dose

For those who opted to participate in the heart rhythm-monitoring subset and completed a minimum of three days of baseline monitoring (day 1 of 2), a second device will be placed on the subject at the conclusion of the second day of the baseline visit (day 2 of 2) after study drug initiation. The device will be worn for 72 hours after which the subject will be instructed to mail the device, identified only by their study subject number, to the vendor for download and generation of a report.

The report will be returned to the enrolling site and any change in the frequency of premature beats or arrhythmias will be shared with the DSMB as summary data in accordance with standard reporting. A change in arrhythmias felt to rise to the level of a serious adverse event will be reported to the Medical Monitor in accordance with serious adverse event reporting (**section 9.3**).

Week 52 Testing

At Week 52, the subject will undergo testing for primary and secondary efficacy endpoints. Testing for this visit will include an exercise test, an echocardiogram, EndoPAT®, BNP, quality of life questionnaires and safety labs. To minimize any potential effect of the timing of administration of the study drug on testing outcomes, the time of the study drug dosing on the visit day will be standardized. Additionally, if a subject is unable to achieve a maximal effort on exercise testing, they will be offered the opportunity to repeat the EST within two weeks (14 days) of the first test. During this time period, the subject should remain on udenafil. If they achieve a maximal effort on this second study, the results of the second study will be used in the analyses.

At Week 52, vital signs (Resting Blood Pressure/Heart rate) will be obtained; assessment of adverse events, concomitant medications, drug accountability and a blood sample will be drawn for determination of udenafil and metabolite concentration immediately following the exercise test. For female subjects, serum or urine pregnancy test will be administered.

Telephone Contact (Between Baseline and Week 52)

Study coordinators will call each subject the day after drug initiation to ensure the study drug is well tolerated. Subjects will be called at weeks 1, 2, 3, 4, 8, 13, 17, 21, 30, 34, 39, 43, 47 to monitor

adherence, to collect medical history data, and record adverse events through 52 weeks. They will also be called 30 and 90 days after Week 52 to record adverse events. Subjects will be encouraged to notify the study coordinator between scheduled contact dates with any new onset symptoms or complications.

Post-Week 52 Follow-up

Option 1: discontinuation of study drug

If a participant chooses to discontinue study drug after Week 52, a study coordinator will call the subject at 30 (week 56) and 90 days (week 64) to record any additional adverse events possibly or probably related to study drug that may have occurred in the 90 days following completion of the study protocol.

Option 2: continuation of study drug for up to 36 additional months

Following the Week 52 visit, participants will have the option of continuing on in FUEL-Extension for up to 36 months. During this time, safety data will be collected. Participants will be contacted by the study coordinator on a quarterly basis to monitor and record adverse events. Once study drug has been discontinued (maximum of 36 months following Week 52), subjects will be contacted at 30 days and 90 days following cessation of study drug to monitor for additional adverse events after discontinuation of drug.

For participants who have completed the 24-month extension and have stopped taking study drug for any period of time prior to re-consenting to version 6, the only testing needed prior to re-initiating study drug is a pregnancy test for female participants.

Table 1. Schedule of Events

Visit Number	1	1	TC1	TC 2-15	2	TC 16-17	TC 16 - 28	
Subject Status	New subject (no FUEL)	Former FUEL subject				Post week 52 Option 1	Post Week 52 Option 2	
Time point	Screening/ Baseline Day 0	Screening/ Baseline Day 0	Day 1	Weeks 1, 2, 3, 4, 8, 13, 17, 21, 30, 34, 39, 43, 47	Week 52	Day 30, 90 post-study (Weeks 56 and 64)	Quarterly	Day 30, 90 post-drug discontinue
Visit Window(s)				± 3 days	± 10 days	± 10 days		
Type of Visit(s)	In-Person	In-Person	Call	Calls*	In-Person	Calls	Calls	Calls
Informed Consent/Assent	X	X						
Subject ID# assigned	X							
Inclusion/Exclusion Criteria	X							
Physical Measurements	X							
Medical history	X							
Demographics/expanded demo	X							
Prior/Concomitant Meds	X			X	X			
EndoPAT®	X				X			
Serum or urine pregnancy test	X	X			X			
Clinical Laboratory tests (creatinine, ALT, AST)	X				X			
Biomarker (BNP) sample	X				X			
Genetic repository sample (optional)	X							
Heart Monitor (optional)	X							
Echocardiogram	X				X			
Exercise test (EST)	X ^a				X ^a			
Dispense Open Label Udenafil ^b	X	X						
Resting BP and HR ^c	X	X			X			
Administer first dose of study drug ^c	X	X						
Peds QL generic and cardiac modules; PCQLI; HAES	X				X			
Drug Accountability ^b	X				X			
Pregnancy counseling (if appl)	X	X		X				
Adverse events assessment		X	X	X	X	X	X	X
Morisky Scale (MMAS)				X				
Schedule/Confirm next visit	X	X	X	X	X			

^a If failed 1st exercise test, exercise testing can be repeated w/in 14 days. Pregnancy testing must also be repeated.^b For detailed Drug Accountability procedures, consult the Manual of Operations (MOO)^c For specific timing of procedures, see Additional Procedures and Measurements in Table 2

Table 2. Initiation of Study Drug

Procedure	Time from administering first dose of study medication			
	<1 hour prior to dose	0 hour	2 hours ± 30 minutes	4 hours ± 30 minutes
Vital Signs (Resting blood pressure and heart rate)	X			X before discharge from clinic
Administer First Dose of Study Drug		X		
Vital Signs Immediately before and Following a 6-minute Self-Limiting Walk			X	
Blood Sample for determination of udenafil and metabolite concentration immediately after the 6-minute walk.			X	
Record Adverse Events		X	X	X
Dispense Initial Study Drug for Home Administration and Discharge from Clinic				X

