6.5 Data Collection

1. Demographic information

The following demographic data will be collected: age, gender, race, ethnicity, cardiac anatomy, date of Fontan, presence of a fenestration, degree of atrioventricular valve regurgitation, grade of ventricular function, concomitant medications, and significant comorbidities.

2. Safety data

Adverse events will be reviewed with each subject at each study visit and during telephone encounters. These events will be recorded and graded by severity and relationship to study drug based on established criteria. Two additional telephone encounters will take place 30 days and 90 days following cessation of study drug [either at Week 52 or up to Week 208 if the subject opts to continue study drug] to assess for any adverse events possibly or probably related to study drug in the period following the completion of study procedures.

3. Exercise stress test

Data from the braked cycle ergometry exercise stress tests will be collected according to protocol established in the PHN Fontan Cross-Sectional Study³.

4. Assessment of ventricular performance

Each study echocardiogram will be stored in a de-identified manner and sent to a core laboratory, which will perform the data analysis and submit the measurements to the PHN Data Coordinating Center (DCC).

5. Vascular function testing

De-identified data from EndoPAT® testing will be collected according to a standardized protocol. These data will be sent to a vascular core lab, which will perform the analysis and submit the measurements to the PHN DCC.

6. Biomarkers

Serum for measurement of BNP level will be sent to a core clinical lab. Results will be sent directly to the PHN DCC.

7. Quality of life survey

Results of the Quality of life surveys will be submitted to the PHN DCC.

8. Samples for the biorepository

Samples collected for the biorepository will be shipped directly to the biorepository for future analysis.

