7.4 Indications for Discontinuation of Study Drug

Study drug may be discontinued temporarily or permanently, but subjects should remain in the trial and complete all study data collection and follow-up measures, including exercise performance testing. Study drug may be discontinued for the following reasons:

- An adverse experience including failure to tolerate study medication that, in the judgment of the investigator or primary physician requires drug discontinuation.
- Voluntary discontinuation of study drug by subject.

When possible, the subject will undergo an exercise test, EndoPAT®, and echocardiogram before permanent discontinuation of the study drug. All information regarding any temporary stop and restart of study drug will be recorded.

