9. SAFETY ASSESSMENTS

9.1 Safety Considerations and Monitoring

The site study coordinators will contact each subject the day after the baseline visit, then weekly for four weeks and monthly until 52 weeks (12 months), and then at 30 and 90 days from the week 52 visit. If the subject is continuing into the extension of up to an additional 36 months then the site study coordinators will contact each subject quarterly until the subject discontinues study drug. At withdrawal or discontinuation, site study coordinators will contact each subject at 30 and 90 days from withdrawal or discontinuation to record adverse events.

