10. STATISTICS

10.1 Primary Aim - Safety

The primary safety outcome is adverse events. The adverse events will be reported by seriousness, severity and relationship with the study drug. Additionally, the number of subjects experiencing a composite outcome of death, heart failure associated hospitalization, or heart transplant will be reported. The overall assessment of safety will be made on the basis of all available adverse events and safety outcome data over the duration of the 12 months extension trial and an additional 90 days following completion of the study protocol.

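### After a first-dose blood-pressure stop, section 6.4 gives new subjects 30 days of adverse-event follow-up and former FUEL subjects 90 days, and sections 9.1 and 7.4 set different rules again

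*Combined protocol and SAP*

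**What the plan says.** Section 6.4 has a baseline-visit description for former FUEL participants and another for subjects who were not in FUEL. Item 5 of each describes the observed first dose and uses the same words for the trigger, "if the subject has a drop in systolic blood pressure > 20 mmHg from the pre- to post-6 minute walk measurement" (or a systolic pressure below an age-based limit), and for the consequence, "they will be excluded from receiving any further study drug". The next sentence differs:

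- Former FUEL subjects: "These subjects will be followed for 90 days per the FUEL protocol for adverse event monitoring".
- New subjects: "These subjects will be followed for 30 days for adverse event monitoring".

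Three other sections bear on what happens once drug is stopped:

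- Section 9.1: "At withdrawal or discontinuation, site study coordinators will contact each subject at 30 and 90 days from withdrawal or discontinuation to record adverse events". It makes no exception for a stop at the first dose.
- Section 7.4, on subjects whose drug is discontinued: "subjects should remain in the trial and complete all study data collection and follow-up measures, including exercise performance testing".
- Section 6.5: "Two additional telephone encounters will take place 30 days and 90 days following cessation of study drug", with a bracketed note that ties cessation to Week 52 or later.

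Section 10.1 bases the primary safety assessment on the 12-month extension and "an additional 90 days following completion of the study protocol".

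**The concern.** Safety is the primary aim and adverse events are its primary outcome. How long a dosed subject is watched for events should therefore be clear and should not depend on how the subject entered the trial. Here one event, with one criterion and one consequence for drug, carries follow-up instructions that disagree, and no reason is stated for the shorter period in new subjects.

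The 30-day sentence is the most specific instruction for a new subject stopped at the first dose, so a site could reasonably treat it as the governing rule. If so, that subject's adverse-event collection ends before a contact that 9.1 requires of everyone. Section 10.1 defines no safety population, does not say whether one-dose subjects are counted, and does not mention unequal observation time. Section 10.4 expects new and rollover subjects not to differ, so the plan does not anticipate a difference in ascertainment between them.

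**Working it through.** There is no figure in the plan to reproduce. The check is a comparison of text followed by day arithmetic.

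**Step 1: is it the same event?** Yes. Item 5 for each entry route in 6.4 has the same blood-pressure criterion and the same withholding of further drug.

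**Step 2: the rules side by side, for a subject stopped on day 0.**

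| Source | Applies to | Follow-up after the stop |
|---|---|---|
| 6.4, non-FUEL item 5 | New subjects | 30 days |
| 6.4, FUEL item 5 | Former FUEL subjects | 90 days |
| 9.1 | Each subject at withdrawal or discontinuation | Contacts at 30 and 90 days |
| 7.4 | Subjects with drug discontinued | All data collection and follow-up |

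For a new subject, the first, third and fourth rows disagree. For a former FUEL subject, the second row fits the third but not the fourth. Section 6.5 adds weaker support for a 90-day contact, because its bracketed text refers to cessation at Week 52 or up to Week 208.

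**Step 3: size of the gap for one subject.**

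- Between the two entry routes, and between the 30-day sentence and the second contact in 9.1: 90 − 30 = 60 days.
- Window described in 10.1, taking 12 months as 52 weeks: 52 × 7 + 90 = 364 + 90 = 454 days.
- Share of that window covered: 30/454 = 6.6% with 30 days, and 90/454 = 19.8% with 90 days.

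Neither period in 6.4 comes close to the full window in 10.1. The 90 days in 10.1 run from completion of the study protocol, not from the last dose. For a subject stopped on day 0, days 31 to 90 lie inside the 12-month period and are not part of that 90-day tail.

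**Step 4: what full follow-up would add.** The telephone schedule in 6.4 has a call on day 1 and at 13 listed weeks, 14 in all. Five fall within 30 days (days 1, 7, 14, 21 and 28). Under 7.4 a further 14 − 5 = 9 calls and the Week 52 visit would remain.

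**Step 5: how many subjects?** The documents give neither the number of new subjects nor the rate of first-dose stops. Section 7.3 expects about 400 FUEL subjects to be available and looks for new ones only if fewer than 300 come from FUEL. With no new subjects, the number affected is 0. As an assumption for illustration only, 100 new subjects and a stop rate of 1% to 5% would give 100 × 0.01 = 1 to 100 × 0.05 = 5.

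**The case against.** The best defence is that the plan already covers these subjects elsewhere. Section 9.1 applies to each subject without exception and 7.4 keeps subjects off drug in the trial, so a site that reads the whole protocol would still make the 90-day contact. This stands as far as it goes: loss of data is one possible result, not a certain one. It does not remove the contradiction, because the specific sentence in 6.4 competes with the general rules.

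Second, the 90 days for former FUEL subjects are attributed to the FUEL protocol, and those subjects come from a six-month randomized trial, whereas a new subject has had a single dose. That may explain the difference between the two routes; the FUEL protocol is not available to check. It does not explain why new subjects depart from 9.1.

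Third, 7.4 does not name the first-dose pressure rule among its reasons for discontinuation. It does name failure to tolerate the drug, and nothing in the plan says these subjects are screen failures. They have been dosed and have had adverse events recorded, and the replacement rule in 7.3 mentions only safety labs and a pregnancy test.

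Fourth, the pressure drop itself is measured in clinic, and events after one dose say little about 12-month safety. This is fair. A reader might infer that the subjects most informative for safety leave early. That is a judgement which the documents do not support beyond acute hypotension.

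**Conclusion.** The operative text contradicts itself on follow-up after a first-dose stop, and the contradiction touches data collection for the primary safety outcome. For a new subject the instructions range from 30 days, through contacts at 30 and 90 days, to all remaining follow-up. If a site follows the 30-day sentence literally, adverse-event collection may end 60 days before the second contact in 9.1, and ascertainment could then differ by entry route.

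Two stronger readings are tempting and should not be drawn:

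- A reader might conclude that events on days 31 to 90 are lost and that the safety summary is biased toward fewer events in new subjects. The documents do not establish this. It depends on sites preferring 6.4 to 9.1 and 7.4, and 10.1 plans no comparison of new with former FUEL subjects.
- A reader might say that two thirds of the safety window goes unobserved (60/90 = 67%). That is a share of the 90-day period after the stop, not of the window in 10.1.

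The likely effect on the overall results is small, because the number affected may be zero or a handful. The point is still worth correcting, since the conflict is plain and concerns the primary aim.

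**What to change.** Reconcile both versions of item 5 in section 6.4 with sections 7.4 and 9.1, so that one follow-up rule applies to every subject stopped at the first dose, whichever way the subject entered. The choice of rule is the sponsor's. Section 7.4 has to be part of the reconciliation: making the two sentences in 6.4 agree with each other and with 9.1 would still leave a conflict with it. If a difference between entry routes is intended, state it as an exception in 9.1 and 7.4 and give the reason.

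Then state in 10.1 that these dosed subjects are counted in the safety summary, and over which window.

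The cost is a few sentences and possibly some added telephone contacts for few subjects. If the sponsor chose full follow-up as in 7.4, each such subject would also have the remaining scheduled calls and the Week 52 visit.
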